All intervention subjects will receive counseling with motivational interviewing in order to achieve compliance.

SREC Dispensing (targeted, but may be revised as needed): Participants will be provided two devices, in case one fails, including charging materials. Based on email and telephone conversations with the SREC manufacturer (NJOY), NIDA, and [name], a Cardiologist and Investigator at McGill University who is currently conducting a randomized clinical trial (Canadian E3 Trial) using a SREC device, we will assume that participants will use one tank/pod every two days (i.e., 0.5 tank/pod per day). At the anticipated rate, there will be 70 days on product or approximately 35 pods required.

Pods will be weighed and logged prior to dispensing. At each visit, the participant will be provided with a sufficient quantity of product for anticipated use and an additional 1 week of product. This will allow the participant to have enough product if the appointment is postponed or the participant uses more than anticipated. At the next visit, the participant will return used and unused product. Returned materials will be weighed. Unused/unopened product will be re-dispensed along with the necessary amount of new product. These estimates will vary depending on individual use. Dispensing will be adjusted to match product use. Participants can contact study staff to request additional product as needed. Participants will be asked to return all unused product and the devices at the end of the study.

Day	Days between visits 7	Pods to be dispensed*
Day 1 (W0) – BR1	7	7
Day 8 (W1) – visit	7	7
Day 15 (W2) – visit	7	7
Day 22 (W3) – visit	7	7
Day 29 (W4) – visit	14	11
Day 43 (W6) – visit	14	11
Day 57 (W8) – visit	14	11
Day 71 (W10) – visit	NA	

\*One week of additional product (~3 or 4 pods) may be distributed at each visit to provide sufficient quantity for any unanticipated use or delay in visit scheduling.

Varenicline dosing and dispensing (targeted, but may be revised as needed): Subjects randomly assigned to the Complete Substitution with the placebo SREC device will be offered up to 12 weeks of varenicline, a nicotinic receptor partial agonist indicated for use as an aid to smoking cessation treatment at no cost. The 12 week

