duration extends the use up to one month after the intervention to be consistent with FDA-approved uses. [name] (or other MD associated with the study) will review all subjects' medical history and evaluate the subject for indications and safety of the varenicline at the BR1 visit prior to the procedure. Subjects may continue in the study if they are not eligible to use varenicline or refuses.

The medication (see below) will be obtained from the OSUWMC or James Cancer Center pharmacy in bulk. Medications will be stored at room temperature (as recommended by the manufacturer) and in locked cabinets.

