#### Bottles

0.5 mg - bottle of 56 NDC 00069-0468-56

1 mg - bottle of 56 NDC 00069-0469-56

Medication will be labeled with the subject's study ID, "For Research Purposes", Study telephone number, Medication Name and strength, Instructions for use, Dispensed date, Expiration date, and Quantity. The research staff dispensing the medication will include their initials on the label and document the dispensation (and return of unused medication) on the product accountability log. Upon completion of the study or if the subject stops taking the medication, any medication that is returned by the subject will be taken to the pharmacy for appropriate disposal.

A general accounting of all varenicline medication obtained from the pharmacy and dispensed to subjects will be maintained by study personnel.

At each visit, the participant will be provided with a sufficient quantity of product for anticipated use and an additional 1 week of medication or given a 4 week card. This will allow the participant to have enough medication if the appointment is postponed. At the next visit, the participant will return unused medication, which will be recorded and redispensed as appropriate. Subjects will be monitored for adverse reaction using the same process as all other arms.

Patients will begin varenicline dosing one week before the day 15 quit date.

Starting Week: 0.5 mg once daily on days 1–3 and 0.5 mg twice daily on days 4–7.

Continuing Weeks: 1 mg twice daily for up to a total of 12 weeks.

Day	Days between visits+7	Daily dose	Tablets to be dispensed
Day 8 (W1) – visit	7 + 7 = 14	0.5 mg once daily for 3 days, then 0.5 mg twice daily for 4 days	22 tablets of 0.5 mg
Day 15 (W2) – visit	7 + 7 = 14	1 mg twice daily	28 tablets of 1 mg
Day 22 (W3) – visit	7 + 7 = 14	1 mg twice daily	28 tablets of 1 mg
Day 29 (W4) – visit	14 + 7 = 21	1 mg twice daily	42 tablets of 1 mg
Day 43 (W6) - visit	14 + 7 = 21	1 mg twice daily	42 tablets of 1 mg
Day 57 (W8) – visit	14 + 7 = 21	1 mg twice daily	42 tablets of 1 mg
Day 71 (W10) – BR2			Up to three weeks (21 tablets) to meet the FDA recommended duration

NRT dosing and dispensing (targeted, but may be revised as needed): Similar to the other conditions, NRT will be dispensed at each visit. Beginning at Day 8 (W1), the participant will be provided with a sufficient quantity of product for anticipated use and an additional 1 week of product. This will allow the participant to have enough

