## d. Data Collection and Management Process

### i. Data to be collected

The schedule of measures is provided in Table 1.

**Baseline/orientation visit:** At the baseline visit, ideally less than two weeks before bronchoscopy, subjects will complete questionnaires, as indicated in Table 1. Exhaled CO , blood pressure, heart rate, oxygen level and height and weight will be assessed.

**Bronchoscopy visits:** At bronchoscopy visits, subjects will complete questionnaires, as indicated in Table 1. Blood pressure, heart rate, oxygen level and weight will be assessed. CO, FeNO and PFTs will be measured. General changes in diet and physical activity over the course of the study will be assessed at the second bronchoscopy visit. Product evaluation will be administered at the follow-up bronchoscopy to assess the experience with the SREC or NRT. Inhalation will be assessed at the follow-up bronchoscopy for subjects assigned to one of the e-cig use conditions, and a nicotine boost will be concurrently assessed for nicotine-SREC users. At the second bronchoscopy visit, the same measures will be provided. These measures are currently used in other studies, including a study involving bronchoscopy.

**Day 8/ Wk1, Day 15/ Wk 2, Day 22/ Wk 3, Day 29/ Wk4, Day 43/ Wk6 and Day 57/ Wk 8 visits:** At each in-person visit, subjects will complete questionnaires, as indicated in Table 1. Blood pressure, heart rate, oxygen level and weight will be assessed. CO will be measured. The product compliance, product accountability log and product evaluation scale will be used to assess the experience with the SREC or NRT.

Phone calls: During the weeks when there are no visits, subjects will be called on the phone to assess tobacco and/or product use, toxicity and health status. Subjects assigned to one of the intervention groups who need additional abstinence counseling beyond the planned visits and calls will be instructed to contact study staff. All subjects will be called within 72 hours post bronchoscopy to monitor symptoms and at 3 months after study completion to assess CESD, Expectancies, Drug Effects/Liking, stages of changes, FTND or modified FTND, as appropriate, product evaluation scale and their tobacco use, including e-cig use.

Daily tobacco use: Subjects will be asked to report their daily tobacco and/or product use by phone or internet.

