**Table 1. Data Collection**

Measures	ORNT	Day 1/ BR1	Day 8/ Wk1	Calls 1-4: Day 4 Day 36 Day 50 Day 64	Day 15/ Wk2 Day 22/ Wk 3 Day 29/ Wk4 Day 43/ Wk 6 Day 57/ Wk8	Day 71/ BR2	3 Months Post BR2 Call
Contact & Physician Information	X						
Demographics	X						
Progress Note	X	X	X	X	X	X	X
Medical History (Baseline and Updates)	X	X	X	X	X	X	
Covid-19 Screener	X						
Covid-19 Follow Up	X	X	X	X	X		
Adverse Events	X	X	X	X	X	X	X
Concomitant Medications	X	X	X	X	X	X	X
Prime MD	X						
CESD	X				Day 29	X	X
SMAST	X						
Perceived Stress		X			Day 29	X	
Perceived Health Risk		X			Day 15	X	
Tobacco Use History*	X						
Social/Lifestyle History	X					X	
Environmental Exposure	X	X			Day 29	X	
Health Changes (Overall Health)**	X	X	X	X	X	X	
Alcohol and Drug Abuse History	X						
Alcohol Use***	X						
Supplements Use	X						
Occupational Exposure	X	X			Day 29	X	
Eligibility Checklist	X						
Smoking Dependence Motives (WISDM)	X		X		X	X	
Stages Of Change	X					X	X
FTND	X	X	X		X	X	X
FTND (Modified for SREC Users)					X (e-Cig)	X (e-Cig)	X (e-Cig)
MN Withdrawal Scale		X	X		X	X	
Smoking Urges		X	X		X	X	
Product Evaluation Scale (NRT)					X	X	X
Evaluation of Electronic Vaping Devices			X	X	X	X	X
Expectancies			X (e-Cig)		X (e-Cig)	X (e-Cig)	X (e-Cig)
Drug Effects/Liking			X (e-Cig)		X (e-Cig)	X (e-Cig)	X (e-Cig)

Interest In Switching or Quitting	X					X	
Vitals (Including Height and Weight)	X	X	X		X	X	
CO (Daily)	X	X	X	X	X	X	
FeNO Results		X				X	
24-Hour Urine Sample Collection Form		X				X	
Inhalation Assessment						X (e-Cig)	
Pulmonary Function Test		X				X	
Sample Collection Form		X				X	
Pre Bronchoscopy Questionnaire		X				X	
Lung Randomization		X				X	
BAL Collection Information		X				X	
Product Accountability Log		X (e-Cig)	X		X	X	
E-cig Cartridge/ Pod Weight Log		X (e-Cig)	X (e-Cig)		X (e-Cig)	X (e-Cig)	
Daily Use Summary (TLFB)	X	X	X	X	X	X	X
Daily Diary		X	X	X	X	X	
Product Compliance****		X (e-Cig)	X	X	X	X	
Cessation Counseling*****			X	X	X	X	X
Follow-Up Call							X
Change In Status	As Needed						
Protocol Deviation Report	As Needed						

\* Subjects will be asked to report their daily tobacco and/or product use by phone or internet

\*\*Similar to Respiratory and Global Health Questionnaire

\*\*\*Follow-up alcohol use is captured on the Daily Use Summary (TLFB)

\*\*\*\*Product Compliance will be administered to SREC subjects starting at BR1; NRT subjects will be asked to complete the questionnaire starting at Day 8/Wk 1

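### Varenicline supplied at the second bronchoscopy (day 71) may be taken to about day 91, but after the 72-hour call the protocol's own schedule has no adverse-event contact until the 3-month call

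*Protocol*

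**What the plan says.** Protocol section 4.c.i (Varenicline dosing and dispensing) states: "Subjects randomly assigned to the Complete Substitution with the placebo SREC device will be offered up to 12 weeks of varenicline". Dosing starts one week before the day 15 quit date, that is, on day 8. Use after the study period is intended, since the 12-week "duration extends the use up to one month after the intervention to be consistent with FDA-approved uses". Uptake is optional: "Subjects may continue in the study if they are not eligible to use varenicline or refuses".

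The dispensing table's entry for day 71 (BR2) is "Up to three weeks (21 tablets) to meet the FDA recommended duration". Leftover tablets may be reused: "At the next visit, the participant will return unused medication, which will be recorded and redispensed as appropriate". For safety follow-up the section says: "Subjects will be monitored for adverse reaction using the same process as all other arms".

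Section 4.d.i (Phone calls) gives the contacts after BR2: "All subjects will be called within 72 hours post bronchoscopy to monitor symptoms and at 3 months after study completion to assess CESD". Section 4.f.vii counts the three months from the second bronchoscopy. In Table 1 the numbered calls are "Calls 1-4: Day 4 Day 36 Day 50 Day 64", all before BR2, and the Adverse Events row is marked at BR2 and next at the 3-month call. The compensation table likewise goes from day 71 straight to the 3-month call. The 72-hour call after BR2 appears only in the text.

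Adverse-event reporting and safety monitoring are referred to an attached DSMP (sections 4.f.ii, 4.f.iv and 4.h), which is not among the documents reviewed.

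**The concern.** A schedule shared by all arms suits products whose supply stops at BR2. SREC devices and unused product are returned then, and no pods are listed for that visit. Varenicline is the one product with a stated supply for use afterwards, so the drug can continue when regular contact has ended.

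Section 4.f.i lists suicidal ideation, seizures, cardiovascular events and serious skin reactions among the reported effects of varenicline. Up to BR2, a subject on the drug has an Adverse Events form every seven days. After the 72-hour call, a reaction that the subject does not report would first be asked about at the 3-month call. The CESD depression scale is not repeated in between, and no scheduled contact confirms that the drug was stopped. What is at stake is the timeliness of safety information in part of one arm.

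**Working it through.** **Inputs.** From Protocol section 4.c.i: start on day 8; maximum 12 weeks (84 days); 1 mg twice daily after the first week; 42 tablets dispensed on day 57; 21 tablets at BR2; call within 72 hours of BR2. From section 4.f.vii: 3-month call counted from BR2. Assumption: three months is 90 days; 84 to 92 days would put the call on days 155 to 163. The ±3-day visit window moves dates slightly and does not change the conclusion.

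**The plan's own figure.** Weeks on drug before BR2: (71 − 8)/7 = 9. Weeks left: 12 − 9 = 3, which matches the stated three weeks. Last dosing day: 8 + 84 − 1 = 91, and also 71 + 21 − 1 = 91. The tablet count does not match: three weeks at two tablets a day needs 42, not 21. Three supply cases are therefore carried through.

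**End of supply.**
- Full three weeks: day 91.
- 21 tablets only: 21/2 = 10.5 days; 71 + 10.5 − 1 = 80.5, about day 81.
- 21 tablets plus the day 57 surplus: 42 − 14 × 2 = 14 left; (21 + 14)/2 = 17.5 days; 71 + 17.5 − 1 = 87.5, about day 88.

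The full three weeks can be reached even with 21 tablets, because the protocol permits a 4-week card in place of counted tablets. A 56-tablet continuing card given on day 57 leaves 56 − 28 = 28 on day 71, and 28 + 21 = 49 exceeds the 42 needed.

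**Gap.** The 72-hour call falls by day 71 + 3 = 74. The 3-month call falls on day 71 + 90 = 161.

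| Case | On-drug days after the 72-hour call | Delay until first asked, as planned | Delay with a call the day after supply ends |
|---|---|---|---|
| Full three weeks | 91 − 74 = 17 | 161 − 91 = 70 to 161 − 75 = 86 days | 1 to 17 days (day 92) |
| 21 tablets + surplus | 88 − 74 = 14 | 161 − 88 = 73 to 86 days | 1 to 14 days (day 89) |
| 21 tablets only | 81 − 74 = 7 | 161 − 81 = 80 to 86 days | 1 to 7 days (day 82) |

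In the full-course case, a further 161 − 91 = 70 days after the last dose pass before the 3-month call.

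**Could other text fill the gap?** The Product use paragraph promises weekly contact, and section 4.d.i promises toxicity calls in weeks without visits. The first belongs to the product-use and run-in text. Table 1 resolves the second to days 4, 36, 50 and 64. Neither creates a contact after BR2.

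**Subjects.** At planned retention, 32 × 0.66 ≈ 21. SAP item 1 calls 66% conservative and expects better, so the ceiling is the whole arm, 32. Uptake is not given. If 25%, 50% or 100% take the drug, that is about 5, 11 or 21 subjects at planned retention, or 8, 16 or 32 at full retention.

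**The case against.** The strongest reply is that the DSMP is where a drug-specific contact would be written, and it has not been seen. That stands. A reader might infer that these subjects go unmonitored after BR2, but the documents do not support this. They show only that the protocol's own schedule lists no contact in that window.

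Real protections also remain: physician review before starting, nine weeks of weekly contact, the 72-hour call, instructions to stop the drug and seek care (sections 4.f.i and 4.f.ii), and a medication label carrying the study telephone number. Adverse Events and Concomitant Medications are both marked at the 3-month call, so late events are still asked about. The documents give no event rate for weeks 10 to 12, so no number of missed events can be claimed. All of this stands and confines the point to timeliness.

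A reader might also infer that an end-of-supply call would catch reactions while the drug could still be stopped. It would not, because it comes after the last dose. For acute events the existing stop-and-call instructions remain the working protection.

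Finally, an extra solicited contact in one arm makes ascertainment unequal between arms. That is a fair cost, dealt with under the fix.

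**Conclusion.** The gap is real on the protocol's own schedule. Subjects supplied with varenicline at BR2 may have 7 to 17 days on drug after the 72-hour call, followed by the period after stopping, with no scheduled adverse-event contact until about day 161. Those days rest on self-report. The range depends on whether dosing follows the stated three weeks or the 21 tablets. The conclusion assumes that the DSMP adds no contact, and it applies only to those who accept varenicline and continue it past BR2: about 21 at planned retention if all do, and never more than 32.

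It would be wrong to read this as a threat to the trial's results. The bronchoscopy, blood, urine and nasal samples are all taken by BR2, so biomarker comparisons are unaffected. This is an inexpensive, optional improvement to safety follow-up and not an error in the analysis.

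**What to change.** For each subject dispensed varenicline at BR2, add one call when the dispensed supply ends (about day 92 at the latest, sooner if the tablets run out sooner), using the Adverse Events and Concomitant Medications forms. Show it in Table 1 and the compensation table, and make any consent-form edit that follows. If the DSMP already schedules such a contact, cross-reference it in Table 1 instead.

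This call gives timely ascertainment and confirms stopping. If the aim is also to detect reactions during dosing, add a brief call about midway through the supply after BR2. Report events from these calls separately from between-arm adverse-event comparisons, because only one arm receives them.

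Cost of the single call at the protocol's $5 per call: 21 × $5 = $105 at planned retention and at most 32 × $5 = $160. Taking the protocol's 30 to 60 minutes per contact (section 4.d.iv) as a generous length, staff time is 10.5 to 21 hours at planned retention and at most 16 to 32 hours, plus repeat attempts to reach subjects. A midway call would at most double these figures. No visit, sample or analysis is added.

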## ii. Timeline

Timetable for completion of study aims: Month	1-2	2-18	18-24
IRB approval, train staff, advertisements, begin enrollment	X		
Accrual		X	
Follow-up procedures		X	X
Analyze data, manuscript preparations			X

## d. Data Collection and Management Process

### i. Data to be collected

The schedule of measures is provided in Table 1.

**Baseline/orientation visit:** At the baseline visit, ideally less than two weeks before bronchoscopy, subjects will complete questionnaires, as indicated in Table 1. Exhaled CO , blood pressure, heart rate, oxygen level and height and weight will be assessed.

**Bronchoscopy visits:** At bronchoscopy visits, subjects will complete questionnaires, as indicated in Table 1. Blood pressure, heart rate, oxygen level and weight will be assessed. CO, FeNO and PFTs will be measured. General changes in diet and physical activity over the course of the study will be assessed at the second bronchoscopy visit. Product evaluation will be administered at the follow-up bronchoscopy to assess the experience with the SREC or NRT. Inhalation will be assessed at the follow-up bronchoscopy for subjects assigned to one of the e-cig use conditions, and a nicotine boost will be concurrently assessed for nicotine-SREC users. At the second bronchoscopy visit, the same measures will be provided. These measures are currently used in other studies, including a study involving bronchoscopy.

**Day 8/ Wk1, Day 15/ Wk 2, Day 22/ Wk 3, Day 29/ Wk4, Day 43/ Wk6 and Day 57/ Wk 8 visits:** At each in-person visit, subjects will complete questionnaires, as indicated in Table 1. Blood pressure, heart rate, oxygen level and weight will be assessed. CO will be measured. The product compliance, product accountability log and product evaluation scale will be used to assess the experience with the SREC or NRT.

Phone calls: During the weeks when there are no visits, subjects will be called on the phone to assess tobacco and/or product use, toxicity and health status. Subjects assigned to one of the intervention groups who need additional abstinence counseling beyond the planned visits and calls will be instructed to contact study staff. All subjects will be called within 72 hours post bronchoscopy to monitor symptoms and at 3 months after study completion to assess CESD, Expectancies, Drug Effects/Liking, stages of changes, FTND or modified FTND, as appropriate, product evaluation scale and their tobacco use, including e-cig use.

Daily tobacco use: Subjects will be asked to report their daily tobacco and/or product use by phone or internet.

**Table 1. Data Collection**

Measures	ORNT	Day 1/ BR1	Day 8/ Wk1	Calls 1-4: Day 4 Day 36 Day 50 Day 64	Day 15/ Wk2 Day 22/ Wk 3 Day 29/ Wk4 Day 43/ Wk 6 Day 57/ Wk8	Day 71/ BR2	3 Months Post BR2 Call
Contact & Physician Information	X						
Demographics	X						
Progress Note	X	X	X	X	X	X	X
Medical History (Baseline and Updates)	X	X	X	X	X	X	
Covid-19 Screener	X						
Covid-19 Follow Up	X	X	X	X	X		
Adverse Events	X	X	X	X	X	X	X
Concomitant Medications	X	X	X	X	X	X	X
Prime MD	X						
CESD	X				Day 29	X	X
SMAST	X						
Perceived Stress		X			Day 29	X	
Perceived Health Risk		X			Day 15	X	
Tobacco Use History*	X						
Social/Lifestyle History	X					X	
Environmental Exposure	X	X			Day 29	X	
Health Changes (Overall Health)**	X	X	X	X	X	X	
Alcohol and Drug Abuse History	X						
Alcohol Use***	X						
Supplements Use	X						
Occupational Exposure	X	X			Day 29	X	
Eligibility Checklist	X						
Smoking Dependence Motives (WISDM)	X		X		X	X	
Stages Of Change	X					X	X
FTND	X	X	X		X	X	X
FTND (Modified for SREC Users)					X (e-Cig)	X (e-Cig)	X (e-Cig)
MN Withdrawal Scale		X	X		X	X	
Smoking Urges		X	X		X	X	
Product Evaluation Scale (NRT)					X	X	X
Evaluation of Electronic Vaping Devices			X	X	X	X	X
Expectancies			X (e-Cig)		X (e-Cig)	X (e-Cig)	X (e-Cig)
Drug Effects/Liking			X (e-Cig)		X (e-Cig)	X (e-Cig)	X (e-Cig)

Interest In Switching or Quitting	X					X	
Vitals (Including Height and Weight)	X	X	X		X	X	
CO (Daily)	X	X	X	X	X	X	
FeNO Results		X				X	
24-Hour Urine Sample Collection Form		X				X	
Inhalation Assessment						X (e-Cig)	
Pulmonary Function Test		X				X	
Sample Collection Form		X				X	
Pre Bronchoscopy Questionnaire		X				X	
Lung Randomization		X				X	
BAL Collection Information		X				X	
Product Accountability Log		X (e-Cig)	X		X	X	
E-cig Cartridge/ Pod Weight Log		X (e-Cig)	X (e-Cig)		X (e-Cig)	X (e-Cig)	
Daily Use Summary (TLFB)	X	X	X	X	X	X	X
Daily Diary		X	X	X	X	X	
Product Compliance****		X (e-Cig)	X	X	X	X	
Cessation Counseling*****			X	X	X	X	X
Follow-Up Call							X
Change In Status	As Needed						
Protocol Deviation Report	As Needed						

\* Subjects will be asked to report their daily tobacco and/or product use by phone or internet

\*\*Similar to Respiratory and Global Health Questionnaire

\*\*\*Follow-up alcohol use is captured on the Daily Use Summary (TLFB)

\*\*\*\*Product Compliance will be administered to SREC subjects starting at BR1; NRT subjects will be asked to complete the questionnaire starting at Day 8/Wk 1

\*\*\*\*\*Cessation counseling will occur at each visit/call after BR1 and/or as often as needed on an individual basis

